## Study Synopsis

Full Title	Validating the Military Service Identification Tool in its ability to correctly identify civilians and those who have served in the military.
Short Title/Acronym	Military Service Identification Tool
Protocol Version number and Date	Version 1 (02/03/2020)
Study Duration	12 months
Study Design	Questionnaire, interview or observation study
Sponsor/Co-sponsors	King's College London
Chief Investigator	[name]
IRAS number	278987
Primary objective	The principal research question is to ascertain whether individuals identified by the Military Service Identification Tool have or have not served in the military (Armed Forces).
Secondary objective (s)	N/A
Number of Subject	Expected sample n=1168. This represents an estimation that 20% of our cohort (n=5844) will have given consent for contact.
Main Inclusion Criteria	Only those participants who formed part of our original study will be screened for eligibility. This corresponds to 2,922 probable veterans and 2,922 civilians. The following inclusion criteria will apply: 1. Participant are listed as 'Alive' in the NIHR Maudsley Biomedical Research Centre Clinical Record Interactive Search database; 2. Participants aged 18 years and older; 3. Participant has given Consent for Contact; 4. Participant has a valid postal address or telephone number; 5. Participants have capacity to consent.
Statistical Methodology and Analysis	Aggregation of data to estimate accuracy of the Military Service Identification Tool

**Glossary of Terms and Abbreviations**

BRC	Biomedical Research Centre
EHR	Electronic Healthcare Record
KCMHR	King's Centre for Military Health Research
MSIT	Military Service Identification Tool
SLaM	South London and Maudsley
UK	United Kingdom

## 1. Introduction

### *Summary of the study:*

Estimates of the UK's military veteran population, defined by the British Government as those who have served in the military for at least one day [1], is approximately 2.5 million, equivalent to around 5% of household residents aged 16 years or over in the UK [2]. UK military veterans receive healthcare provision from the National Health Service (NHS), with care recorded in local, regional and national EHRs [3]. EHRs – structured and unstructured (i.e. free text) – can be used to evaluate disease prevalence, surveillance, to perform epidemiological analyses and investigate quality of care and to improve clinical decision-making [4], [5].

There is no national marker in UK EHRs to identify veterans, nor is there a requirement for healthcare professionals to record it, making it difficult to evaluate the unique healthcare needs of those who have served in the UK Armed Forces [6]. This study, funded by Forces in Mind Trust, seeks to validate the Military Service Identification Tool, an open-source computer program that searches through free-text clinical notes to make a prediction on a person's military status. It is in the public interest to know the health of our Armed Forces. The Tool has been validated using manually annotated datasets, but we now need to validate an individual's military status by contacting them via post or telephone and asking, "Have you ever served in the Armed Forces". The research team will work closely with the CRIS Patient Advisor Group and local healthcare professionals.

### *The current study:*

Currently, there is no military service marker in electronic healthcare records to identify who is a veteran in England and Wales [3]. This makes it difficult to evaluate the unique healthcare needs of those who have served in the UK military. In a previous study, we set out to investigate whether it was feasible to identify veterans who accessed secondary mental healthcare services via their anonymized electronic healthcare records using a manual, text search based, method. To do this, we used the SLaM BRC Case Register. This is a novel data resource, derived directly from the routine electronic healthcare records of the SLaM NHS Foundation Trust. SLaM is one of Europe's largest mental health providers, serving over 1.2 million residents in four South London boroughs. This Case Register holds patient's electronic healthcare records for all secondary mental healthcare provisions within SLaM. All these electronic healthcare records have been anonymized and a system has been developed to enable researchers to access and search through these records called the clinical record interactive system (CRIS).

As part of the first study we developed a manual, text search based, method using commonly used terms and phrases found in the free text clinical notes to identify veterans. Running this manual method resulted in the identification of  $n = 6,039$  potential veteran records, of which  $n = 1,600$  were selected to scrutinize in more detail, whilst considering time and manpower restrictions. This resulted in  $n = 693$  veteran records, suggesting an identification rate of 43% when using the manual method. Therefore, we concluded that it was feasible to identify veterans in electronic healthcare records, but time consuming. Each potential veteran record was manually verified by the research team by reading through each patient's notes. This took on average 11 minutes per record.

To address the time it took to identify veterans and improve sensitivity and reach we developed the MSIT, and it proved to be quicker, more accurate and cheaper than the manual method. The Tool was designed to detect military service, not just veteran status. We took a systematic approach to developing and testing the MSIT. We used different subsets of all the electronic healthcare records available to us, to ensure the MSIT was developed and trained on a different set of electronic healthcare records (named the training dataset). Subsequently the MSIT was verified on another subset of the data (named the gold standard dataset) to ensure it would still be able to identify veterans if a different set of electronic healthcare records would be used.

We managed to identify 2,922 veterans in the electronic healthcare records when applying MSIT to inspect 150,000 individual records. The MSIT took only 20 minutes to go through all these records and had an identification rate of 88% when compared to the manual approach. We also matched these veterans to 2,922 non-veterans based on age and gender to compare their mental health treatment pathways.

Despite the success of our initial developments we have faced a significant barrier that may prevent the widespread, dissemination, roll-out and implementation of the MSIT. Various academics and stakeholders (e.g. NHS England,

Cobseo) are interested in the MSIT. However, they have highlighted an important limitation, namely it is still unclear whether the veterans identified by the MSIT are ‘actual’ veterans. MSIT identifies veterans based on the notes provided by the clinician in the electronic healthcare record. It is also important to understand if higher rates of physical and mental health are represented in a veteran population compared to civilians. By including both samples – civilian and veteran – we’re ensuring that fair comparisons are able to be made. This There is currently no opportunity to verify their veteran status. For example, no service number is provided in their medical records.

Therefore, to overcome these limitations and to demonstrate that the MSIT is correctly identifying military service (serving personnel, veterans or civilian) it is important to reach out to those who have been identified to ask about their previous Service.

## 2 Study Objectives and Design

### 2.1. Study Objectives

The principal research aim is to ascertain whether individuals identified by the MSIT have or have not served in the military (Armed Forces). This study will ask up to 5 questions to eligible participants, with the responses used to validate the MSIT algorithm predictive ability.

*Primary Outcome:*

The primary outcome of interest will be the military serving status of participants. We will use the information provided to cross-check the performance of the MSIT. Where incorrect classifications have been performed, refinement of the algorithm will take place to improve the accuracy. The questions that will be asked have been designed to elicit as descriptive information as possible to help us refine the MSIT in the event it has made an incorrect prediction.

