### 2.2 Study Design & Flowchart

The study will employ a questionnaire approach by asking a set of (up to 5) questions on previous military service. These questions are as follows:

Question 1: Have you ever served in the Armed Forces?

- Yes
- No

Question 2: Which part of the Armed Forces did you serve in?

- Royal Navy
- Royal Marines
- Army
- Royal Air Force

Question 3: What was the highest rank when you left the military?

- Senior Commissioned Officer (Cdr/Lt Col/Wg Cdr and above)
- Commissioned Officer (to Lt Cdr/Maj/Sqn Ldr)
- Senior Non-Commissioned Officer
- Junior Non-Commissioned Officer
- Other ranks (AB/Pte/AC/JT or equivalent)
- Other (please specify)

Question 4: How long did you serve in the Armed Forces?

Question 5: When you left the Armed Forces, were you:

- Regular
- Reserve
- Both

If the participant responds NO to Question 1, the questionnaire will end. If they answer YES, they will be asked questions relayed to military service. The participant can skip any question. These questions will be asked only once. No follow-up will be performed. Participants who take part in the study will be asked to supply an email address at the end of the questionnaire to enter a prize draw. This is voluntary. If they decide to take part, they will be entered a prize draw. At the end of the study, we will randomly select the winners. The prizes are: 1 £50 Amazon Gift voucher, 5 £25 Amazon Gift voucher and 20 £10 Amazon Gift voucher.

The study is using a cross-section, single point in time, questionnaire approach. There is no control comparison group, or randomised group allocation.

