#### *Participant Eligibility:*

Only those participants who formed part of our original study will be screened for eligibility. This corresponds to 2,922 probable veterans and 2,922 civilians.

The following inclusion criteria will apply:

1. Participant are listed as ‘Alive’ in the SLaM BRC Clinical Record Interactive Search database;
2. Participants will be aged 18 years and old;
3. Participant has given Consent for Contact;
4. Participant has a valid postal address or telephone number;
5. Participants have capacity to consent.

The following exclusion criteria will apply:

Participants will be excluded if a clinician is required to be notified of the research prior to contact, as this may indicate at risk participants. Further participants who are not fluent in spoken English will be unable to take part in the study due to inability to understand the participant information and consent form. Therefore, non-English speaking participants will not be included in this study.

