## **8. Data Handling**

Data collected for this study will be encrypted and stored on a secure server maintained by the sponsor organisation and will not identifiable by participant name. The bespoke website for this study will be developed prior to data collection and will use servers located in London, England. The information stored on this system will be:

1. Proxy ID: A unique identifier will be created to allow users to ‘log-in’ and complete the questionnaire. The mapping key to link responses and contact details will be held by the SLaM BRC Research Administrator.
2. Questionnaire responses: Participant questionnaire responses will be recorded in the system and will be saved with the ‘proxy id’ identifier.
3. Prize draw: Participants are able to provide an email address to enter the prize draw. This will be saved in a separate database. At no time will the ‘proxy id’ and email address be linked.

Upon completion of data collection, all data will be downloaded from the server and the server be decommissioned. At any time, up until data analysis, participants can withdraw from the study.

The research team will keep legible and accurate documents to ensure thorough documentation of study conduct. The highest degree of confidentiality will be maintained for managing data collected throughout the course of the study. However, to meet legal responsibilities we will permit authorised representatives of the health authorities to examine records, to satisfy quality assurance reviews, audits and evaluations of study safety and progress.

For data analysis, the non-identifiable data acquired will be downloaded and stored on a secure network managed by SLaM BRC. Only the immediate research team will have access to data collected with the Chief Investigator [name] being the custodian of the data. Data will be used to assess the performance of MSIT, and further refine the Tool to improve classification rates.

This study will be compliant with the principles of the Declaration of Helsinki, compliant with the Data Protection Act (2018) and follow local and national regulations.

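### Does using the same survey responses both to assess MSIT and to refine it make the accuracy result optimistic?

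*Protocol*

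**What the plan says.** Section 2.1 (Study Objectives) gives the responses a validation role, "with the responses used to validate the MSIT algorithm predictive ability", and repeats it under the primary outcome: "We will use the information provided to cross-check the performance of the MSIT". The next sentence adds the second role: "Where incorrect classifications have been performed, refinement of the algorithm will take place to improve the accuracy". The questionnaire was written with that in mind: "The questions that will be asked have been designed to elicit as descriptive information as possible to help us refine the MSIT".

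Section 8 (Data Handling) puts both roles in one sentence: "Data will be used to assess the performance of MSIT, and further refine the Tool to improve classification rates".

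Two further statements limit the data. Section 2.2 says: "These questions will be asked only once. No follow-up will be performed". Section 3, under Participant Eligibility, says: "Only those participants who formed part of our original study will be screened for eligibility".

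The Study Synopsis lists one objective, whether the people MSIT identified have or have not served, and gives the secondary objectives as N/A. Its analysis line is an estimate of the tool's accuracy. The protocol nowhere says that a refined version will be scored or reported on these responses. It also reserves no part of them for testing one.

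**The concern.** Using one dataset to find a classifier's errors, correct them and then measure the corrected classifier is a standard source of optimism. Changes that happen to suit these respondents count as improvement even if they would do nothing for anyone else.

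Several features make the worry reasonable here. Refinement is a stated purpose, and the questions were designed to support it. Self-report is collected once from a closed cohort, so the study supplies no fresh respondents. Once every error has been inspected, an untouched subset cannot be recovered. The Introduction also reports that MSIT was originally trained on one set of records and verified on another, a separation that is not repeated here.

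At stake would be any claim that refinement had raised accuracy against self-report, the reference this study exists to obtain. Stakeholders who already doubt whether the identified veterans are real ones could raise the same doubt about the refined tool.

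**Working it through.** **1. The plan's own figure.** The cohort is 2,922 + 2,922 = 5,844 (Section 3). With 20% expected to have Consent for Contact, 0.20 × 5,844 = 1,168.8, which the synopsis gives as 1,168. This is a ceiling on respondents, because not everyone contacted will answer. The protocol gives no response rate. I take 100%, 50% and 20% as assumptions, so N = 1,168, 584 and 234.

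**2. Which estimate could be biased.**

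- *Existing MSIT.* Its labels come from the earlier study and were fixed before any response. Comparing fixed labels with later answers involves no selection on those answers. Refining the tool afterwards cannot change that comparison.
- *Refined MSIT.* If it is scored on the responses that guided the refinement, the result is optimistic. The protocol states the refinement but not the scoring.

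**3. How large the optimism could be, if the scoring were done.** Assume K candidate variants, each relabelling a share f of respondents, with every relabel equally likely to be right or wrong. The true gain is then 0. The best variant on the same data is kept, and the spurious gain is the mean of the largest net gain divided by N. Simulation gives, in percentage points:

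| Assumption | N = 1,168 | N = 584 | N = 234 |
|---|---|---|---|
| K = 5, f = 5% | 0.76 | 1.08 | 1.69 |
| K = 20, f = 5% | 1.22 | 1.73 | 2.73 |
| K = 20, f = 5%, all within one shared 10% of respondents | about 0.9 | about 1.2 | about 1.9 |

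With K = 20, moving f from 2% to 10% gives 0.77 to 1.72 points at N = 1,168 and 1.73 to 3.87 at N = 234.

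A different model gives other sizes. Suppose accuracy is 88%. This borrows the identification rate against the manual approach, which is not accuracy against self-report. If half of the 12% errors are patched, apparent accuracy is 88 + 6 = 94%. If 25% to 75% of that correction carries over to new records, true accuracy is 89.5% to 92.5%, so the optimism is 4.5 to 1.5 points. The direction is firm; the size is not.

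**4. What a hold-out would buy.** Reserve one third of respondents: n = 389, 195 or 78. With 5% of labels changed and no true gain, the standard error of the gain is √(0.05/n). At n = 389 this is √(0.05/389) = 0.0113, or 1.13 points. The 95% half-width, 1.96 × √(0.05/n), is 2.2, 3.1 and 5.0 points for the three sizes. Scoring all respondents would give 1.3, 1.8 and 2.9.

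Set against this the root-mean-square error of the uncorrected gain around its true value of 0, at N = 1,168:

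| Estimate of the gain | Root-mean-square error (points) |
|---|---|
| Uncorrected, 5 variants | 0.88 |
| Uncorrected, 20 overlapping variants | 1.01 |
| Uncorrected, 20 independent variants | 1.27 |
| One-third hold-out (unbiased) | 1.13 |

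The hold-out has the larger total error in two of the three settings and a slightly smaller one in the third. The ordering is the same at 584 and 234. It would also leave fewer errors from which to refine the tool.

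**The case for a change.** The strongest case for a change is about timing. The dual use is fixed in the protocol and is not merely left open. A hold-out works only if it is drawn before the errors are examined, and cross-validation works only if every refinement step can be repeated in each fold. The safeguard would therefore belong beside the refinement sentence in Section 2.1, and it would cost the primary result no respondents.

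The mechanism stands, and so does the point about order. The need for a protocol change does not. Nothing in the protocol forbids a split, and an analysis plan written before the errors are examined could set one, or could choose an optimism correction instead. The assess-and-refine sentence in Section 8 reads naturally as two successive steps, and learning from a validation set's errors after reporting them is ordinary practice. Naming a frozen version would be tidy but would change no result, because the labels already exist. Cross-validation presupposes automated refinement, whereas Section 2.1 describes questions meant "to help us refine the MSIT in the event it has made an incorrect prediction", which may equally mean reading individual cases. Having no second self-report sample is a limit on what this study can show about a later tool. It is not an error in what it sets out to show.

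**Conclusion.** No change is needed. Followed as written, the plan gives an estimate for the existing MSIT that refinement does not bias, and that estimate answers the sole objective. The risk is conditional on a step the protocol does not plan: reporting a refined version's accuracy on the same respondents without correction.

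If that step were taken, the result would be optimistic by roughly 1 to 4 points. That range depends on assumed numbers of variants, relabelling shares, carry-over and response rates, none of which the protocol gives. The one remedy that would alter conduct, a one-third hold-out, exchanges this bias for a half-width of 2.2 to 5.0 points and does not clearly give a better estimate. Analysts would meet the point sensibly by reporting the existing tool first and describing any refined result on these responses as apparent and exploratory. A clarifying sentence in Section 2.1 would do no harm, but no conclusion depends on it.

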### 2.2 Study Design & Flowchart

The study will employ a questionnaire approach by asking a set of (up to 5) questions on previous military service. These questions are as follows:

Question 1: Have you ever served in the Armed Forces?

- Yes
- No

Question 2: Which part of the Armed Forces did you serve in?

- Royal Navy
- Royal Marines
- Army
- Royal Air Force

Question 3: What was the highest rank when you left the military?

- Senior Commissioned Officer (Cdr/Lt Col/Wg Cdr and above)
- Commissioned Officer (to Lt Cdr/Maj/Sqn Ldr)
- Senior Non-Commissioned Officer
- Junior Non-Commissioned Officer
- Other ranks (AB/Pte/AC/JT or equivalent)
- Other (please specify)

Question 4: How long did you serve in the Armed Forces?

Question 5: When you left the Armed Forces, were you:

- Regular
- Reserve
- Both

If the participant responds NO to Question 1, the questionnaire will end. If they answer YES, they will be asked questions relayed to military service. The participant can skip any question. These questions will be asked only once. No follow-up will be performed. Participants who take part in the study will be asked to supply an email address at the end of the questionnaire to enter a prize draw. This is voluntary. If they decide to take part, they will be entered a prize draw. At the end of the study, we will randomly select the winners. The prizes are: 1 £50 Amazon Gift voucher, 5 £25 Amazon Gift voucher and 20 £10 Amazon Gift voucher.

The study is using a cross-section, single point in time, questionnaire approach. There is no control comparison group, or randomised group allocation.

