##### *Informed Consent Procedures:*

Once eligible participants have been identified a Post-Doctoral Research Associate (to be appointed) will, in the first instance, send an email to the participant informing them of the study and asking for consent to the main research question (question 1). Informed content will be obtained prior to any questionnaires or procedures being employed. This will be performed either via the study website or via telephone. Time and date of consent will be recorded alongside a unique study identifier. Participants will be informed that participant is voluntary, that non-participant or withdrawal from the study will not affect their medical care in anyway. Prior to consent being sought, participants will be given time to read and consider the Participant Information Sheet.

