##### *Treatments and Follow-up:*

This study does not seek to test any intervention or treatment. We will not perform any follow-up, nor require the participant to provide any further information above and beyond the questionnaire.

*End of Study Definition:*

Once all participants have been contacted using the stated procedure, or after 12 months, whichever comes first, the study will be defined as complete. Participants who have provided an email address will be randomised and winners selected. They will be contacted within 3 months of the study completing.

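### Does ending the questionnaire at NO defeat the aim of refining the MSIT after an incorrect prediction?

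*Protocol*

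**What the plan says.** Section 2.1 (Study Objectives, Primary Outcome) makes serving status the primary outcome. It adds that the questions were "designed to elicit as descriptive information as possible to help us refine the MSIT in the event it has made an incorrect prediction". It does not separate the two kinds of error.

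Section 2.2 (Study Design & Flowchart) lists five questions. Question 1 asks whether the person ever served. Questions 2 to 5 cover branch, rank, length of service, and regular or reserve status. The branching rule is "If the participant responds NO to Question 1, the questionnaire will end". Only those who answer YES see the rest, and any question may be skipped. The section also states: "These questions will be asked only once. No follow-up will be performed". Section 4 (Treatments and Follow-up) repeats this: "We will not perform any follow-up, nor require the participant to provide any further information above and beyond the questionnaire".

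Section 8 (Data Handling) names both uses of the answers: "Data will be used to assess the performance of MSIT, and further refine the Tool to improve classification rates". On how the tool works, the Introduction says that it "searches through free-text clinical notes to make a prediction" (Summary of the study), and that "MSIT identifies veterans based on the notes provided by the clinician in the electronic healthcare record" (The current study). The Study Synopsis lists no secondary objective.

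**The concern.** The tool can be wrong in two ways. It can miss someone who served (false negative), or flag someone who did not (false positive). Section 2.1 reads as if the questions would describe both. Under the branching rule they describe only the first, and the ban on follow-up means that nothing more can be asked of the second group later.

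The false positive is also the error behind the doubt reported in the Introduction, where outside parties ask whether those flagged are really veterans. If refinement depended on participants explaining such errors, for instance through a relative's service or civilian work with the forces, the one contact with each person would be lost. No analysis plan could recover answers that were never collected.

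**Working it through.** **1. The plan's own figure.** The cohort is 2 × 2,922 = 5,844 (section 3, Sample Size). At 20% consent for contact, 0.20 × 5,844 = 1,168.8, stated as 1168 in the Study Synopsis. The figure reproduces, rounded down. The concern does not depend on it.

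**2. Following the branches.**

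| MSIT prediction | Answer to Question 1 | Cell | Questions shown |
|---|---|---|---|
| Served | YES | True positive | 1 to 5 |
| Not served | YES | False negative | 1 to 5 |
| Not served | NO | True negative | 1 only |
| Served | NO | False positive | 1 only |

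Of the two error cells, only false negatives can give descriptive answers.

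**3. Does the accuracy estimate depend on Questions 2 to 5?** Each person's cell is fixed by the MSIT prediction, known beforehand, and the answer to Question 1. Positive and negative predictive value and overall agreement are ratios of these four counts. Questions 2 to 5 enter none of them, so the stop at NO changes no estimate.

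**4. How many people stop after a label?** The protocol gives no predictive value against self-report and no response rate, so both are assumptions here. The 88% in the Introduction is an identification rate against the manual approach and is not a predictive value against self-report. Applying the 20% equally to both groups gives 0.20 × 2,922 = 584.4 contactable people in each.

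False positives = 584.4 × r × (1 − PPV), where r is the response proportion and PPV the positive predictive value:

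| PPV (assumed) | r = 1 | r = 0.5 | r = 0.25 |
|---|---|---|---|
| 0.95 | 29 | 15 | 7 |
| 0.88 | 70 | 35 | 18 |
| 0.70 | 175 | 88 | 44 |

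False negatives at full response, with negative predictive value (NPV) in this matched sample assumed to be 0.90 to 0.99, are 584.4 × 0.10 = 58 down to 584.4 × 0.01 = 6. False positives are then between 29/(29 + 58) = 33% and 175/(175 + 6) = 97% of all errors. The group without description could be small or could be most of the errors.

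**5. Who would answer an extra item for NO respondents?** Let f be the fraction of tool-negatives who did serve, assumed 0 to 0.10. The number answering NO is 584.4 × [(1 − f) + (1 − PPV)]. At full response this runs from 584.4 × (0.90 + 0.05) = 555 to 584.4 × (1.00 + 0.30) = 760.

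The false-positive share is (1 − PPV)/[(1 − PPV) + (1 − f)]. It runs from 0.05/1.05 = 4.8% to 0.30/1.20 = 25%. The other 75% to 95% are civilians whom the tool classified correctly.

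**6. What refinement needs.** The tool predicts from clinicians' free text. To correct a false positive, the developers need to know that the prediction was wrong and which text produced it. Question 1 gives the first, and the existing record holds the second. A participant's account of a possible reason could add colour, but it could not show which note misled the tool.

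**The case for a change.** The best case for a change is textual. Section 2.1 credits the questions, not the notes, with describing incorrect predictions, and it does not limit this to one error type. The protocol nowhere says that false positives will go to record review. One skippable tick-box shown to every NO respondent would not reveal the tool's prediction, and would keep those respondents to two questions, within the five questions and 15 minutes that the protocol allows. Failing that, the sentence could be narrowed at almost no cost.

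The textual point stands: the sentence promises somewhat more than the branching can deliver. The rest is weaker. The wording states an aim, and it is accurate for false negatives. Someone who never served has no branch, rank or length of service to report, so stopping there is ordinary skip logic and a fair choice on burden. The likely causes of false positives that an item would list appear nowhere in the protocol. The item would also need an amended questionnaire and probably new consent wording, since the Informed Consent Procedures describe "asking for consent to the main research question (question 1"). How the developers work through misclassified records is detail that a protocol commonly leaves to other documents.

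**Conclusion.** No change is called for. A gap exists between the stated purpose in section 2.1 and the branching in section 2.2: false positives yield a corrected label only. Its effect on the sole stated objective, and on every accuracy measure, is nil, because Question 1 alone fills the table. That conclusion rests on the questionnaire logic and on no assumed rate.

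The number of people affected, about 7 to 175 across the assumed predictive values and response proportions, describes who is asked no more. It does not measure bias or lost precision in any planned estimate.

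For the refinement aim, the conclusion assumes that the team can return to the notes behind each misclassified record, as the description of the tool implies. A further item would be a preference with limited return, and narrowing the sentence in section 2.1 would tidy the text without altering any result.

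### Question 1, the only check on MSIT, does not say that any length of service or reserve service counts, and a misread NO cannot be detected from the questionnaire

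*Protocol*

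**What the plan says.** Section 2.2 of the Protocol lists up to five questions. The first, "Question 1: Have you ever served in the Armed Forces", has the answers Yes and No. It gives no minimum length of service and does not mention reserves. Two later items touch on these matters: "Question 4: How long did you serve in the Armed Forces" and "Question 5: When you left the Armed Forces, were you", the latter offering regular, reserve or both. Only people who answered YES reach them, because "If the participant responds NO to Question 1, the questionnaire will end". The same section adds: "These questions will be asked only once. No follow-up will be performed".

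The Introduction (Summary of the study) describes veterans as "defined by the British Government as those who have served in the military for at least one day". Under The current study, the Introduction says that the tool was built to detect military service in general, not only veteran status.

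Section 2.1 gives the use of the answers: "We will use the information provided to cross-check the performance of the MSIT". It says that incorrect classifications will lead to refinement of the algorithm, and that the questions were designed to draw out descriptive detail "to help us refine the MSIT in the event it has made an incorrect prediction".

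**The concern.** Question 1 alone decides whether a person counts as having served, so any error in it becomes an apparent error, or an apparent success, of the tool. Someone who served briefly, or only in the reserves, may not regard that as having served and may answer NO. The item does nothing to correct that impression, and the later questions that would are never shown to that person.

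The routing also works against the purpose stated in section 2.1. A flagged person who answers NO is exactly the apparent incorrect prediction for which descriptive detail is wanted, yet the questionnaire stops there. A genuine false positive and a correctly flagged person who misread the question leave the same record.

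Two things are at stake. The first is the accuracy estimate: misreading moves PPV in one direction only, downwards, and more replies do not remove the bias. The second is refinement: apparent false positives that are really correct detections of brief or reserve service may be among the cases used to revise the algorithm.

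**Working it through.** **Inputs from the Protocol**
- Groups: 2,922 probable veterans and 2,922 matched probable civilians (section 3).
- Expected share with Consent for Contact: 20%. Expected sample: 1168 (Study Synopsis).
- Identification rate of 88% against the manual method (section 1, The current study). The Protocol does not call this a PPV. It is used below only as an illustrative true PPV.

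**The plan's own figure.** 0.20 × (2,922 + 2,922) = 0.20 × 5,844 = 1,168.8, which agrees with the stated 1168. Per group, 0.20 × 2,922 = 584.4, or about 584. This is a ceiling on flagged respondents, since it takes everyone with Consent for Contact to be otherwise eligible and to reply.

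**Assumptions.** Let u be the share of people who truly served but answer NO. The documents give no value, so u is varied from 1% to 10%. True PPV is varied from 80% to 95% and true NPV from 90% to 98%. The Protocol states neither.

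**Flagged group**
- Observed PPV = PPV × (1 − u).
- Relabelled flags = n × PPV × u.
- Apparent false positives = n × (1 − PPV) + relabelled flags.

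With n = 584 and PPV = 0.88, truly serving respondents number 584 × 0.88 = 513.9 and genuine false positives 584 × 0.12 = 70.1.

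| u | Observed PPV | Relabelled flags | Share of apparent false positives that are spurious |
|---|---|---|---|
| 1% | 0.88 × 0.99 = 87.1% | 5.1 | 6.8% |
| 2% | 0.88 × 0.98 = 86.2% | 10.3 | 12.8% |
| 5% | 0.88 × 0.95 = 83.6% | 25.7 | 26.8% |
| 10% | 0.88 × 0.90 = 79.2% | 51.4 | 42.3% |

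The 95% interval half-width is 1.96 × √(0.88 × 0.12 / 584) = 0.026, or 2.6 points. The bias is 0.88 × u, which reaches 2.6 points at u of about 3%. With fewer replies the interval widens and the relabelled count falls in proportion, but the bias in percentage points stays the same.

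Over the whole range (PPV 80% to 95%, u 1% to 10%), about 5 to 56 flags are relabelled and PPV falls by 0.8 to 9.5 points.

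**Predicted-civilian group**
- Observed NPV = NPV + (1 − NPV) × u.
- At NPV 95% and u = 10%: 0.95 + 0.05 × 0.10 = 95.5%, with 584 × 0.05 × 0.10 = 2.9 missed cases counted as correct.
- Over the whole range (NPV 90% to 98%, u 1% to 10%) the rise is 0.02 to 1.0 point.

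**The case against.** The strongest reply is that the question is plain and matches the study's aim, which is whether people have served. Taken literally, ever having served covers a single day and covers the reserves. A reader might infer that Question 1 contradicts the Protocol's own definition of a veteran. It does not. The one-day rule is cited in the Introduction as the Government's definition, the Protocol does not adopt it as a scoring rule, and the question is consistent with it. What remains is a risk of misreading, for which the documents give no rate. All of this stands.

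Three further readings go beyond the text:
- That every short-service or reserve member who answers NO counts as a tool error. This is true only of flagged respondents. In the predicted-civilian group the same answer counts as a correct classification.
- That such cases are lost for good. They cannot be detected from the questionnaire, but section 8 describes a key linking responses to contact details, and clinical notes could in principle be re-read. No such step is planned.
- That refinement will train the tool away from brief or reserve service. Section 2.1 says that refinement follows incorrect classifications. It does not say that a NO is used automatically as a training label.

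Participants also read an information sheet before consent (section 4), and its text is not available here. The omission is therefore established for the wording of Question 1, not for everything a participant sees.

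These replies limit the claim without removing it. The item that settles each person's status could be misread in a predictable way, and the routing collects nothing that would show it.

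**Conclusion.** The point holds as a weakness in the reference-standard item, not as a contradiction. If people with brief or reserve service misread Question 1, PPV is biased downwards and NPV slightly upwards, and analysis of the answers cannot correct either.

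The direction follows from the text; the frequency is unknown. In the central illustration, misreading by 2% to 10% of those who truly served lowers PPV by 1.8 to 8.8 points (88% minus 86.2% and 79.2%), while NPV moves by at most 1.0 point over the range examined. These sizes rest on an assumed u, an assumed true PPV and NPV and, for the counts, full eligibility and reply. The upper end would need both a sizeable brief-service or reserve share and frequent NO answers within it, and the documents evidence neither. The case for acting is that prevention is very cheap, not that a large bias has been shown.

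**What to change.** Add one sentence to Question 1, identically on the website and in the telephone script: *Please answer Yes if you served for any length of time (at least one day), as a regular or a reserve.* The yes/no format and the routing can stay. The Protocol does not say whether time in training counts, so the sponsor should decide this and word the item accordingly.

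The cost is slightly longer question text, with no added items or contacts. Section 8 says that the website is to be developed before data collection, so the change can be made at that stage. The sentence makes misreading less likely but does not detect any that remains, so a report of PPV should still note this limitation.
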